12. RESEARCH STRATEGY

12.1 SIGNIFICANCE

12.1.1. Ongoing Importance of physical activity for CV disease prevention in T2D The prevalence of diabetes mellitus has more than tripled in the past 30 years, and currently affects 25.8 million Americans.⁶ T2D accounts for >90% of prevalent diabetes cases in adults.⁷ Because people with T2D are at very high risk for CV disease, people with T2D are a high priority NHLBI study population.⁸⁻¹¹ Several large observational studies support regular physical activity as a potent therapy to reduce CV mortality in people with T2D.¹²⁻¹⁵ A recent meta-analysis of prospective cohort studies found improved CV outcomes in participants with diabetes by physical activity strata (HR = 0.61 (0.47-0.80) for CV mortality for highest vs. lowest physical activity levels).¹⁶ Data from RCTs have been mixed, as lower stroke event rates (HR = 0.62 (0.35-0.98) were observed in the intervention vs. placebo group of an RCT of a behavioral intervention that increased physical activity¹⁷, but the Look AHEAD study was stopped for lack of group differences in CV outcomes¹⁸. Lower than expected CV outcomes in both Look AHEAD

study groups may have under-powered this study to detect an intervention effect.¹⁸

[figure not shown]
Overall, the consistent benefits of regular physical activity with regard to cardiorespiratory fitness, CV mortality, and all-cause mortality that have been observed in large cohort studies provide a convincing evidence base that regular physical activity improves CV health. Also, one study found mean annual health costs were ~\$2000 less in people with T2D who performed physical activity ≥ 2 times/week vs. <1 time/week.¹⁹ Thus, regular physical activity, a critical cornerstone of T2D treatment, may actually generate cost savings.²⁰

12.1.2. Why improve function? PFLs predict disability, loss of independence, and premature mortality for adults.²¹⁻²³ Regular physical activity can preserve function and reduce these adverse outcomes.²⁴⁻²⁷

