In addition to behavioral counseling targeting SCT constructs (Figure 4 in Significance), counselors will assist participants in the intervention group to set specific goals for physical activity in a paper log and on an electronic FitBit activity tracking device (see Appendix). Participants will record their actual physical activity next to their goals for easy review during counseling visits. Health promotion clinic staff will encourage participants to advance goals towards meeting U.S. physical activity guidelines of 150 minutes/week of moderate intensity activity (e.g., brisk walking) and 2-3 days/week of strength activities consisting of cycles of 5-10 repetitions of sit-to-stand, toe stand, chair dip, and side step-down (see Appendix).⁷⁵ Although achieving guidelines is a long-term physical activity goal, counselors will help patients to work towards this goal systematically but gradually. Participants and counselors will determine each person’s rate of physical activity increase to accommodate unique factors associated with their T2D, functional limitations, and fitness.

12.3g. USUAL CARE GROUP

Participants in the usual care arm will receive three mailings during the intervention phase (Table 7). Health promotion clinic staff will mail materials from the Center for Disease Control and Prevention website that address general healthy aging topics: i.e., advanced directive care planning, vision and hearing changes with aging, respectively. These mailings will be the only research contacts with participants during the 12-week intervention phase.

Table 8 Study visit activities, by study group

Visit	Phase	Intervention	Usual Care
1	Enrollment	Consent, baseline testing	Same as intervention arm
2-3	Baseline time (t) = 0 weeks	Baseline covariate and outcome testing	Same as intervention arm
4	t = 2 weeks	In-person clinic visit * with phone counseling†	None
5	t = 4 weeks	Phone counseling†	Print mailing on aging topic
6	t = 6 weeks	In-person clinic visit * with phone counseling†	None
7	t = 8 weeks	Phone counseling†	Print mailing on aging topic
8	t = 10 weeks	In-person clinic visit * with phone counseling†	None
9	t = 12 weeks	Phone counseling†	Print mailing on aging topic
10-11	Exit testing, t = 3 months	Exit covariate and outcome testing	Same as intervention arm

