Summary: Taken together the preliminary data collected support the idea that an intervention in a clinical setting which allows for screening to identify appropriate patients and then implementing a clinic based intervention has the potential to improve physical activity and function in sedentary adults with T2D.

12.3i. OUTCOME MEASURES (see Table 10 on next page)

12.3j. POWER CALCULATION AND DATA ANALYSES FOR AIM 1 (EFFECTIVENESS)

Power Calculation: We used PASS version 11 to calculate power for the physical activity outcome.⁷⁸ Aim 1 was powered based on a previously observed effect size of Cohen's $d = .61$ when comparing a physical activity intervention to an education control group on physical activity of moderate-to-vigorous intensity⁷⁹ among older, obese adults. Assuming similar sized effects in the current study and a two-sided alpha of 0.05, the proposed sample size of $n=90$ will provide over 80% power to detect differences between the activity intervention and usual care for Hypothesis 1. If our effects match that of our preliminary data (increase in combined moderate-vigorous physical activity levels by 142 minutes/week across 3 participants (from 65 ± 80 to 207 ± 87 minutes/week, mean \pm SD), then we will have over 95% power to detect differences between the activity intervention and usual care. Enrollment of $n=130$ was planned to allow for up to 30% attrition. For Aim 1b, the proposed sample size will be sufficient to obtain stable means and standard deviations in order to calculate an accurate effect size estimate for physical function outcomes.

Data analysis: Before conducting the analyses by aim, we will assess descriptively and graphically the mean and distribution of each study outcome and covariate, in order to assess for outliers and skewed distributions. If variables are not normally distributed, we will consider logarithmic transformation.

Aim 1 Data Analysis

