Objective physical activity	Actigraph GT3x+ accelerometer measures physical activity objectively as minutes/week of moderate intensity and vigorous intensity physical activity, respectively. ⁸⁰ We define moderate intensity levels by the methods of Freedson et al. ⁸¹ Participants will wear the Actigraph for a 7-day period pre/post intervention. We will ensure measurement during a typical 7-day period and will use standard wear-time validation procedures to ensure valid weekday and weekend data. Actigraph data will be collected on the 7 days between physical function and VO ₂ max testing.	Continuous	Aim 1 1° outcome
Physical activity behavioral constructs from SCT	Standard survey measures to assess the following physical activity behavior assessments of constructs from SCT: Self-efficacy to do physical activity of increasing duration; ^{82,83} Social-environmental support is a valid measure of how others support one's healthy lifestyle choices; ⁸⁴ Lower barrier scores on the Dishman physical activity barriers survey are associated with higher levels of physical activity; ⁷⁷ Physical Activity outcome expectancy for elders survey includes positive elements of physical activity for older adults, including health-related factors – better scores are associated with higher physical activity levels ⁸⁵	Continuous	Aim 1 Predictor variable: physical activity (PA predictor)
Physical Function outcomes			
Cardiorespiratory fitness (VO ₂ max)	To assess cardiorespiratory fitness, we measure breath-by-breath utilization of oxygen (VO ₂) and carbon dioxide (VCO ₂) with a Medgraphics Ultima CPX metabolic cart (Minneapolis, MN). We also measure blood pressure (auscultation), and cardiac status (12-lead ECG). To determine VO ₂ max, subjects perform treadmill exercise to exhaustion using a standard protocol. ^{86,87} We define VO ₂ max per standard practice. ⁸⁶	Continuous	Aim 1 2° outcome
Physical function	400-meter rapid gait speed test measures fitness and mobility; it is sensitive to change for adults with minimal to mild functional impairment ; predicts disability and mortality. ⁸⁸ Physical function measures will be assessed on a separate study date from the VO ₂ max testing.	Continuous	Aim 1 2° outcome

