Physical function	The Short Physical Performance Battery (SPPB) measures function with the following valid subscales: balance, usual walking speed, and repeated chair rise. The SPPB is sensitive to change for adults with moderate to severe functional impairment , and predicts disability and mortality. ^{68,89}	Ordinal, range 0-12	Aim 1 2° outcome
Lower extremity strength	Lower extremity strength will be measured as leg extensor (quadriceps) and leg flexor (hamstring) strength using [name] laboratory's established techniques. ^{38,90}	Continuous	Aim 1 Function predictor
Grip strength	Hand grip strength will be measured by dynamometer. ⁹¹	Continuous	Aim 1 2° outcome
Metabolic control outcome			
Hemoglobin A1c	Average glycemic control measured by standard methods ⁹²	Continuous	Aim 1
Covariates for adjustment			
Depression symptoms	Center for Epidemiologic Studies Depression Scale measures depressive affect severity and is valid in people with ^{93,94} and without T2D. ^{95,96}	Continuous	Aim 1 covariate for adjustment
Lower extremity arthritis pain symptoms	Western Ontario and McMaster Universities Arthritis Index—valid measure of knee and hip pain and stiffness. ⁹⁷	Continuous	Aim 1 covariate
Cognitive processing speed	Stroop test –measures cognitive processing speed as a valid predictor of cognitive function in adults with and without T2D. ⁹⁸⁻¹⁰⁰	Continuous	Aim 1 covariate

DEXA scan	DEXA will allow the calculation of body composition as fat-free mass and total mass so that we may report exercise performance levels standardized to these body composition measures.	Continuous	VO ₂ max covariate for adjustment
Cognitive executive function	Behavioral Dyscontrol Scale – valid measure of executive function in adults with and without T2D. ^{101,102}	Continuous	Aim 1 covariate
Process outcomes			
Acceptability	Percent of intervention patients who would recommend intervention ¹⁰³ ; Percent of clinical providers/staff who recommend continuing to offer the intervention to patients ¹⁰³	Percentile	Aim 2
Time burden	Patient time required for each intervention visit ¹⁰³ ; Staff/provider time required for each intervention visit ¹⁰³	Continuous	Aim 2
Safety outcomes			
	Participant report of outcomes after baseline testing: falls, musculoskeletal injuries, foot ulcers, hypoglycemia ^{20,24,57}	Continuous	Safety

12.3k. ANALYSIS OF ACCEPTABILITY OUTCOMES (Aim 2 and Safety analysis)

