Safety analysis: For ethical reasons, in addition to the acceptability outcomes addressed in Aim 2, we will monitor for study group differences in safety-related outcomes, in order to assess for any potential study harm. We selected the following safety outcomes based on relevant use in prior trials and per expert description of safety concerns in T2D; falls, musculoskeletal injuries, severe hypoglycemia (glucose <60 mg/dl or hospitalization/Emergency department visit for hypoglycemia).^{20,24,57} At study exit visit 9, we will ask participants if any of the following safety-related outcomes occurred since baseline testing was completed in visit 2: fall requiring clinical evaluation; fall that did not require clinical evaluation; musculoskeletal injury requiring clinical evaluation; musculoskeletal injury that did not require clinical evaluation; severe hypoglycemia (glucose <60 mg/dl or clinical evaluation for hypoglycemia), foot ulceration. For each safety outcome measured, we will descriptively report these as both dichotomous outcomes (Yes/No) as well as the frequency of safety events (e.g., number of hypoglycemic episodes). We will use ANCOVA to obtain preliminary data on the group differences in safety outcomes with adjustment for baseline conditions that may increase safety risk. Baseline conditions that may increase safety risk include the following: baseline moderate-to-severe impairment on SPPB (baseline score <10), prior history of fall, slowed cognitive processing speed).

12.3l POTENTIAL PROBLEMS AND ALTERNATIVE STRATEGIES We have planned alternatives for potential problems that may arise. For example, if participants report new medical concerns or symptoms during the telephone counseling sessions with the health promotion clinical staff, staff members will transfer the patient to the clinic triage nurse to evaluate the patient's symptoms. Also, if participants report new musculoskeletal pains to the health promotion clinic staff, the staff member will send an electronic health record note to the physician assistant conducting the in-person treatment visits to advise the patient on any recommended treatment or activity restrictions.

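### Safety outcomes rest on participant report at one exit visit, with no rule for people who miss it, so events may be under-counted and the arm comparison biased in either direction

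*Combined protocol and SAP*

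**What the plan says.** Section 12.3k gives one collection point for safety outcomes, which it numbers as exit visit 9: "we will ask participants if any of the following safety-related outcomes occurred since baseline testing was completed in visit 2". The matching row of Table 10 reads "Participant report of outcomes after baseline testing: falls, musculoskeletal injuries, foot ulcers, hypoglycemia". The question list in 12.3k covers falls and musculoskeletal injuries (each with or without clinical evaluation), severe hypoglycemia and foot ulceration. Reporting is descriptive, with one arm comparison: "We will use ANCOVA to obtain preliminary data on the group differences in safety outcomes with adjustment for baseline conditions that may increase safety risk".

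Other sections determine who can be asked, and when:

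- Section 12.3j says that enrollment of 130 "was planned to allow for up to 30% attrition".
- Section 12.3g says of usual care: "These mailings will be the only research contacts with participants during the 12-week intervention phase".
- In the intervention arm, 12.3f and Table 8 have a physician assistant check for safety concerns at visits 4, 6 and 8. Section 12.3l sends new symptoms to a triage nurse, and new musculoskeletal pain to the physician assistant by a health-record note.
- The missing-data plan sits under Hypothesis 1 in 12.3j and concerns physical activity.
- Section 12.3e and Table 8 place exit testing at visits 10-11. In Table 8, visit 9 is a counseling call (intervention) or a mailing (usual care).

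**The concern.** Someone who leaves before exit testing is never asked the safety questions. In an activity trial a fall, an injury, a foot ulcer or hypoglycemia is a plausible reason for leaving, so the people who are not asked may have had more of the events being counted. The plan states no withdrawal call, record check or rule for non-attenders that feeds the safety outcome, and it does not extend the Hypothesis 1 missing-data plan to safety.

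Section 12.3k gives the detection of possible harm as the reason for this comparison. If it includes only people who attend exit, event counts may be too low and the arm difference may be distorted. The visit number adds a practical problem: read literally, visit 9 gives usual-care participants no contact at which they could be asked.

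**Working it through.** **The plan's own figures.** From 12.3j: 90 analyzed, 130 enrolled, up to 30% attrition. 90 / (1 − 0.30) = 128.6, so 129, against 130 stated. The figures agree. The ceiling on people without exit data is 0.30 × 130 = 39, or 19 to 20 per arm under 1:1 allocation. The documents give no figure for the safety comparison.

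**Inputs for the illustration.** The documents give neither event rates nor the share of people who leave after an event. I assume a true risk p of 15% (intervention) and 8% (usual care), 30% dropout without an event, and dropout L after an event of 30% (unrelated to the event), 50% or 60%.

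**Formula.** Risk seen among exit attenders = p(1 − L) / [p(1 − L) + (1 − p)(0.70)].

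- Intervention, L = 0.30: 15.0%
- Intervention, L = 0.50: 0.075 / (0.075 + 0.595) = 11.2%
- Intervention, L = 0.60: 0.060 / (0.060 + 0.595) = 9.2%
- Usual care, L = 0.30: 8.0%
- Usual care, L = 0.50: 0.040 / (0.040 + 0.644) = 5.8%
- Usual care, L = 0.60: 0.032 / (0.032 + 0.644) = 4.7%

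**Arm difference seen (true value 7.0 points), computed before rounding.**

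| Where event-related loss occurs | L = 50% | L = 60% |
|---|---|---|
| Neither arm | 7.0 | 7.0 |
| Both arms equally | 5.3 | 4.4 |
| Intervention only | 3.2 | 1.2 |
| Usual care only | 9.2 | 10.3 |

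These settings put intervention-arm dropout slightly above the planned ceiling: 0.15 × 0.50 + 0.85 × 0.30 = 33.0%, or 34.5% with L = 60%. Holding each arm at exactly 30% overall, the risk seen is p(1 − L) / 0.70. With intervention-only loss the difference is then 10.7 − 8.0 = 2.7 or 8.6 − 8.0 = 0.6 points, so the conclusion does not depend on this.

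**No true difference.** With 15% risk in both arms, 30% overall dropout and L = 60%, an affected arm shows 0.15 × 0.40 / 0.70 = 8.6%. The apparent difference is −6.4 points if only the intervention arm is affected, 0.0 if both are, and +6.4 if only usual care is.

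**Precision.** With all 65 per arm ascertained at 15% and 8%, the standard error is √(0.15 × 0.85/65 + 0.08 × 0.92/65) = 0.0556. The 95% interval is about ±11 points, and power is about 24% by the normal approximation.

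**The case against.** The strongest reply is that the consequence is limited. The analysis is labelled preliminary and mostly descriptive, and a ±11-point interval means the trial would usually show no clear excess even with complete data. That stands, and it limits the weight of the point. It does not justify leaving out people who may have left because of an event.

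Second, 30% is a planning ceiling, and the plan intends high retention. Nothing says that a person who stops counseling is not invited to exit testing. That also stands: 39 is a maximum, and a reader should not infer that 39 people will lack safety data.

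Third, the intervention arm has interim safety checks and triage. A reader might infer that an injury in someone who withdraws goes wholly unrecorded. The documents do not support this: clinic staff may well record it, and the public text refers to other parts, such as an Appendix, that it does not contain. But no section carries these findings into the safety outcome. If they were carried in, capture would be unequal, because usual care has no such visits, and apparent harm in the intervention arm could be inflated.

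Fourth, the list omits cardiovascular events, although 12.1.1 says "Because people with T2D are at very high risk for CV disease" and, in the fitness test of Table 10, "subjects perform treadmill exercise to exhaustion using a standard protocol". That test is done in both arms with blood pressure and ECG measurement, so it does not by itself suggest an arm difference. Section 12.3k says that its outcomes were chosen from prior trials and expert description. The omission is therefore an optional extension of the point.

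**Conclusion.** The point holds in this form. The safety comparison rests on participant report at one exit visit, up to 30% of the 130 randomized (at most about 39) may not reach it, and no other source or rule is stated for them. Events may be under-counted, and the arm difference may be biased in either direction. The bias is toward safety if event-related loss is greater in the intervention arm, or if that loss is equal in both arms and a true excess exists. It runs the other way if usual care loses more people after events.

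A reader might infer that the comparison is necessarily biased toward safety, or that half to four-fifths of a true excess disappears. The documents do not show the direction, and the larger loss (7.0 points falling to 3.2 or 1.2) needs event-related dropout in the intervention arm only. With equal event-related loss the fall is to 5.3 or 4.4 points, about a quarter to over a third. All of these sizes rest on assumed rates. The gap is inexpensive to close, so the change is worth making even for a preliminary analysis.

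**What to change.** In 12.3k and Table 10:

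1. Ask the same safety question list by phone, at withdrawal or at 3 months, of every randomized participant in either arm who does not attend exit testing.
2. Report by randomized arm with all randomized as the denominator, and state the number not reached in each arm, so that they are not silently counted as event-free.
3. Reconcile the visit number in 12.3k with 12.3e and Table 8.
4. Optionally, add a health-record check over the same fixed window in both arms, limited to emergency visits, hospitalizations and deaths. This would also show all-cause and cardiovascular hospital events, which the current list omits. An unrestricted query would pick up the billed intervention visits and counselor notes that exist in one arm only.

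If a separate monitoring plan already covers non-attenders, it is enough for 12.3k to cite it and state the denominator.

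The cost is a short call script for non-attenders, with matching protocol and consent wording, plus one record query if the option is taken. Sample size and visits do not change. Some people will still be unreachable, a record check would miss care outside the health system, and the comparison will remain imprecise.

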*Clinic visit is to teach and monitor form for strength exercises, to assess for safety concerns during treatment, and to coordinate with health promotion clinic staff counselor (see Figure 3 in Significance)

†Phone counseling delivered by health promotion clinic staff

12.3h. PRELIMINARY DATA PERTINENT TO THE APPLICATION

I and other study team members have collected study data in primary care clinical settings and clinical trial settings that demonstrate the feasibility of collecting the proposed measures. In addition, these data suggest that the proposed screening and behavioral intervention can be implemented in primary care systems that use health promotion clinic staff. Finally, these data suggest that the proposed intervention will improve the proposed physical activity measures that are strongly linked to physical function.

Preliminary data – Behavioral counseling by health promotion clinic staff I led an RCT for patients with uncontrolled hypertension of an intervention that included health promotion clinic staff counseling. Health promotion clinic staff called intervention patients and delivered brief, tailored counseling about lifestyle measures to control blood pressure, and arranged a primary care clinic visit.⁵⁴ We did not contact usual care patients. Because this intervention improved process outcomes related to blood pressure control and had high acceptability to patients and clinicians,⁵⁴ our clinics have continued this hypertension management process.

Table 9 Population Characteristics for Preliminary Data on Correlations between Physical Function and Physical Activity	
	Overweight, sedentary adults (n = 12)
T2D (%)	58
Age (years, mean (SD))	61.1 (5.4)
BMI (kg/m ² , mean (SD))	30.2 (2.6)
Accelerometer-measured Physical activity (Combined moderate-vigorous intensity minutes/week, mean (SD))	91.0 (97.3)
Cardiorespiratory fitness (maximal oxygen uptake, ml/kg/min)	21.9 (1.5)
Physical function: Rapid, timed 400-meter walk, seconds (mean, SD)	300.4 (56.7)

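### Section 12.3k grades falls and injuries by an undefined need for clinical evaluation, while scheduled clinician checks and symptom routing exist only in the intervention arm, so the graded categories can differ between arms with no true difference in harm

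*Combined protocol and SAP*

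**What the plan says.** Section 12.3k (Safety analysis) puts one set of questions to participants at exit: "we will ask participants if any of the following safety-related outcomes occurred since baseline testing was completed in visit 2". Falls are recorded as "fall requiring clinical evaluation; fall that did not require clinical evaluation", and injuries as "musculoskeletal injury requiring clinical evaluation; musculoskeletal injury that did not require clinical evaluation". The same list includes "severe hypoglycemia (glucose <60 mg/dl or clinical evaluation for hypoglycemia), foot ulceration". Earlier in the section, severe hypoglycemia is defined by the same glucose threshold or by a hospitalization or emergency department visit. Each outcome is to be reported as yes/no and as a count. ANCOVA then gives preliminary group differences, adjusted for baseline risk: SPPB impairment, earlier falls and slow processing speed.

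Contact during the 12 weeks differs by arm. Table 8 gives the intervention arm counseling at Visits 4 to 9 and in-person clinic visits at Visits 4, 6 and 8. Its footnote says that one purpose of the clinic visits is "to assess for safety concerns during treatment". Under 12.3l, when new medical concerns or symptoms come up in a call, "staff members will transfer the patient to the clinic triage nurse to evaluate the patient's symptoms". For new musculoskeletal pain, "the staff member will send an electronic health record note to the physician assistant conducting the in-person treatment visits to advise the patient". For usual care, 12.3g describes three mailings and adds: "These mailings will be the only research contacts with participants during the 12-week intervention phase".

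**The concern.** The only severity grade for falls and injuries is whether the event needed clinical evaluation. Participants assign it themselves, with no definition, and the plan describes no adjudication. In one arm the protocol supplies occasions for a clinician to look at an event. In the other, evaluation depends on the participant seeking care. Two people with the same sore knee could therefore answer the exit question differently because of their arm and not because of the injury.

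At stake is how the trial reads harm. An apparent excess of evaluated injuries in the activity arm could reflect closer contact. The ANCOVA covariates cannot correct this, because they are measured at baseline and the contact difference arises after randomization. The hypoglycemia item is more exposed: under the exit question, evaluation alone can decide whether an episode counts as severe. Section 12.3f also names hypoglycemia among the things the physician assistant looks for, and those visits exist in the intervention arm only. The primary outcome is not affected.

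**Working it through.** The plan states no safety event rate, evaluation rate or safety sample size, so there is no figure to reproduce. The working below sizes the mechanism under assumptions.

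**Inputs**
- From the documents: 1:1 allocation, and 90 participants in the power calculation of 12.3j, so 90 / 2 = 45 per arm.
- Assumed: the true proportion with an injury is *p* = 20% in both arms.
- Assumed: the share of injured people who seek evaluation themselves is *s* = 0.30 in both arms (range 0.20 to 0.50).
- Assumed: *r*, from 0.1 to 1.0, is the share of the remaining intervention-arm events that are evaluated through the study and then reported at exit as requiring evaluation.
- Assumed: the exit questions are put to both arms at exit testing. (12.3k calls this Visit 9, whereas Table 8 places exit testing at Visits 10-11.)

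**Formulas**
- Evaluated category, usual care: *p* × *s* = 0.20 × 0.30 = 6%.
- Evaluated category, intervention: *p* × [*s* + (1 − *s*) × *r*].
- Non-evaluated category: *p* × (1 − *s*) = 0.20 × 0.70 = 14% in usual care, and *p* × (1 − *s*) × (1 − *r*) in intervention.

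| *r* | Evaluated, intervention vs usual care | Ratio | People per 45 | Non-evaluated, intervention vs usual care |
|---|---|---|---|---|
| 0.1 | 7.4% vs 6% | 1.23 | 3.3 vs 2.7 | 12.6% vs 14% |
| 0.2 | 8.8% vs 6% | 1.47 | 4.0 vs 2.7 | 11.2% vs 14% |
| 0.5 | 13% vs 6% | 2.17 | 5.9 vs 2.7 | 7% vs 14% |
| 1.0 | 20% vs 6% | 3.33 | 9.0 vs 2.7 | 0% vs 14% |

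Worked line for *r* = 0.5: 0.20 × (0.30 + 0.70 × 0.5) = 0.20 × 0.65 = 0.13, and 0.13 / 0.06 = 2.17.

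The ratio is [*s* + (1 − *s*) × *r*] / *s* and does not depend on *p*. At *s* = 0.50 it runs from 0.55 / 0.50 = 1.1 to 1.00 / 0.50 = 2.0. At *s* = 0.20 it runs from 0.28 / 0.20 = 1.4 to 1.00 / 0.20 = 5.0.

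**Chance of a nominally significant difference.** With 45 per arm and a two-sided 5% test, 10% vs 6% is declared different about 10% of the time, and 14% vs 6% about 24% of the time. In the formula above these correspond to *r* = (0.50 − 0.30) / 0.70 = 0.29 and *r* = (0.70 − 0.30) / 0.70 = 0.57. Both use a normal approximation with few events, so they are rough.

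**All events combined.** In every row the two categories sum to 20% in each arm. Regrading alone cannot move that total, provided both arms report events equally.

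**The case against.** The strongest reply is that *requiring* ordinarily means need. A strain glanced at during a scheduled visit did not plainly require evaluation, and a participant who reads the question that way grades it the same in either arm. That reading is legitimate. But the plan does not define the term, and 12.3l itself describes the triage nurse's task as evaluating symptoms, so the other reading is open too.

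The routing is also weaker than it may look. For musculoskeletal pain, 12.3l has the physician assistant advise the patient; evaluation is the word used only for triage of new medical concerns or symptoms. Falls are not mentioned there, so a symptom-free stumble reaches a clinician only through the general safety check at Visits 4, 6 and 8. The case is therefore thinner for falls than for injuries, and shares near *r* = 1.0 are extreme.

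The plan also contains part of the remedy. Table 10 and the first list in 12.3k name falls and injuries unsplit, the exit questions record both categories, and nothing says that ANCOVA will be run on the evaluated category alone. A careful reader could see an excess in one category offset by a deficit in the other. This stands, but the plan does not say that the combined total is the comparison that counts.

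Finally, the safety comparison is labelled preliminary, with no hypothesis or threshold attached, and 12.3m does not tie the future trial to these counts. That limits the consequence.

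**Conclusion.** The plan as written permits a between-arm difference in the evaluated and non-evaluated categories that comes from contact and not from harm. This depends on participants treating an evaluation that took place as one that was required. Its size cannot be computed from the documents. Under the assumptions above, the spurious ratio for evaluated injuries is about 1.2 to 3.3 at *s* = 0.30, and 1.1 to 5.0 over the wider range of *s*. At the low end that is less than one extra person per 45.

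A reader might infer more: that the severity grade is confounded with arm by design, or that the trial will report excess harm. The documents do not support either, because the term can be read as need and no routed share is given. Nor is usual care without contact: it receives the mailings and the same exit testing, and its members remain clinic patients who can seek care. The point is a correctable ambiguity in the safety comparison.

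**What to change.** In 12.3k:

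1. Name all falls and all musculoskeletal injuries, evaluated or not, as the main between-arm safety comparison.
2. Define the evaluated category in the exit question, and report the split descriptively by arm, with a caveat that it depends on contact.
3. For each evaluation, record whether the participant or the study initiated it. Flag study-initiated ones; do not exclude them. A contact at Visits 4, 6 or 8, or a triage transfer, may replace care that the participant would otherwise have sought. Excluding these would downgrade real events in the intervention arm only and could understate harm.
4. Reconcile the two definitions of severe hypoglycemia. The one in the exit question is exposed to the same contact difference.

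The cost is a few sentences in 12.3k and one added item on the exit form; the data for the combined comparison are already collected. The downsides are that the combined outcome mixes minor with more serious events, and that closer contact may still affect recall in the intervention arm. The split stays in the report for the first reason, and the second should be stated as a limitation.
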